5.2 Study Visits

The schedule of visits and main procedures at each visit are summarised in the study flowchart (see Section 3.1). If the time buffers of the visits are utilised, later visits must be shifted accordingly.

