5.2.5.2 Week 14 (Day 42 \pm 5) - Part B only

Safety assessments

- clinical laboratory tests (biochemistry, haematology and urinalysis)

5.2.6 Visit 3

During Visit 3, a patient may be hospitalised on Day 1 for 24 hours and up to Day 4. The duration of the hospital stay is left at the discretion of the investigator and will depend on the individual subject and the regulatory requirements at the study site. Later assessments may be performed on an outpatient basis.

5.2.6.1 Visit 3, Day 1 (Week 8 (+2 Weeks or Up to +4 Weeks in Case of AEs which have Not Adequately Recovered))

Visit 3, Day 1, should take place 8 weeks after Visit 2 (+2 weeks or up to +4 weeks in case of AEs which have not adequately recovered). This should be Week 16 (+2 weeks or up to +4 weeks in case of AEs which have not adequately recovered), otherwise Week 16 should be changed to the appropriate week number.

Safety assessments (predosing, results must be checked before ¹⁷⁷Lu-OPS201 administration; can be performed one day before)

- physical examination
- weight
- vital signs and 12-lead ECG
- performance status
- clinical laboratory tests (biochemistry, haematology, and urinalysis)
- serum or urine pregnancy test for women of childbearing potential (not surgically sterile or 2 years postmenopausal).
- AEs/concomitant medications
- control of withdrawal from treatment criteria (see Section 6.4)
- 24 hour ECG (Holter) (start before amino acid infusion).

Efficacy assessments

- survival
- quality of life questionnaire (QLQ-C30; GI.NET21)
- tumour markers
- CT/MRI (same method as in Screening Visit); +2 weeks or up to +4 weeks in case of AEs

Exploratory biomarkers

CCI

Administration of ¹⁷⁷Lu-OPS201

See Section 6.2.

Safety assessments (postdosing)

- vital signs (stop of infusion, 30±5 minutes 60±10 minutes, 4 hours ±10 minutes)
- AEs/concomitant medications.

Dosimetric measurements

- blood sampling before and at stop of infusion, 1 hour ±5 minutes, 4 hours ±10 minutes
- whole body imaging at 4 hours ±10 minutes
- SPECT/CT imaging (Part B only) at 4 hours ±10 minutes.

*5.2.6.2 Visit 3, Day 2***Safety assessments at 24 hours \pm 1 hour**

- clinical laboratory tests (biochemistry, haematology)
- vital signs
- AEs/concomitant medications.

Dosimetric measurements at 24 hours \pm 1 hour

- blood sampling
- whole body imaging
- SPECT/CT imaging.

*5.2.6.3 Visit 3, Day 3***Safety assessments at 48 hours \pm 1 hour**

- clinical laboratory tests (biochemistry, haematology)

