5.2.8 End of Core-trial Visit

The EOCT Visit should take place 8 weeks after Visit 3. This should be Week 24 (Day 1 \pm 5) if no previous visit window was extended. Subjects who are to receive additional cycles of therapy will undergo the EOCT assessment after Cycle 3. Where possible, the EOCT visit and Visit 4, Day 1 (additional cycle) can be combined. An additional EOAC assessment will be done 8 weeks after the last dose of therapy (Part B only).

Safety assessments (at EOCT/EOAC Visit)

- vital signs and 12-lead ECG
- physical examination
- weight
- performance status
- clinical laboratory tests (biochemistry, haematology, pituitary markers and urinalysis)
- AEs/concomitant medications (see Section 8.1.4.1).

Efficacy assessments (at EOCT/EOAC Visit)

- CT/MRI (same method as in Screening Visit); ± 5 days' window acceptable
- quality of life questionnaire (QLQ-C30; GI.NET21)
- survival

- tumour markers.

CCI

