Visit 3: 8 weeks after Visit 2 Day 1 (+2 weeks or up to +4 weeks in case of AEs which have not adequately recovered), subjects will receive a CT/MRI scan to monitor the RECIST v1.1 status and tumour volume. Subjects will then receive the third administration of ¹⁷⁷Lu-OPS201 followed by safety and dosimetry evaluations over 8 days, with additional laboratory safety test repeated at Day 15 (±2 days). At Week 4 (Day 29±5 days) Week 6 (Day 42±5 days) (Follow-up Visit 3) and at intermediate timepoints, the safety of the subjects will be monitored.

EOCT Visit: 8 weeks (±5 days) after Visit 3 Day 1, the safety and efficacy of the treatment will be evaluated. Subjects will receive a CT/MRI scan to monitor the RECIST v1.1 status and tumour volume.

Subjects who are to receive additional cycles of therapy will undergo the EOCT assessment after Cycle 3. Where possible, the EOCT visit and Visit 4, Day 1 of the first additional cycle can be combined.

Figure 1 Overview of Study Design for Part A and Part B and Post Study Follow-up

EOCT=end of core trial; W=weeks, * Only for Part B.

[figure not shown]

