1.3 Methods and procedures

1.3.1 Study treatment

1.3.1.1 Treatment of subjects

Subjects will be treated with three cycles and may receive up to 2 additional cycles (Part B only) of ^{177}Lu -OPS201 PRRT with an interval of 8 weeks +2 weeks, or up to +4 weeks in case of AEs which have not adequately recovered. If any side effects are adequately recovered within the 4 weeks, the next treatment cycle can be initiated; if not, no further PRRT treatment will be administered and the subject will undergo the EOCT (or EOAC) Visit followed by the Long-term Follow-up Visits.

The absorbed organ doses (blood and image based), especially the bone marrow and kidney doses as a limiting organs, will be analysed after each treatment cycle so that the radioactivity for the following cycles for this particular subject can be reduced in order to not exceed cumulative absorbed organ dose limits.

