3.2.14 Visit windows

All data will be organised and analysed according to the scheduled visits outlined in the protocol. However, actual observation times may differ from the scheduled visit times and where this occurs the results should be allocated to the most appropriate visit. Therefore, time intervals (e.g. visit windows) have been constructed so that every observation collected can be allocated to a particular time point. If more than one record occurs within the same visit window where only one assessment is expected then the following rule should be applied: for pre-study assessments the last non-missing result prior to study drug administration should be used; for post-treatment assessments the closest non-missing result to the scheduled visit should be used.

Study part	Scheduled visit	Time interval (days)	
Pre treatment (Screening)	Screening Visit	Week – 4 to -1	
Active phase	Visit 1, Day 1	Day 1 (Week 0)	
	Visit 1, Day 2	Day 2	
	Visit 1, Day 3	Day 3	
	Visit 1, Day 4	Day 4(-Day 5)	
	Visit 1, Day 7	Day 7(- Day 8)	
	Visit 1, Day 15	Day 15 ±2 days	
	Follow-up 1 Visit 1	Week 4 (Day 29 ±5 days)	
	Follow-up 2 Visit 1 – Part B only	Week 6 (Day 42±5 days)	
	Visit 2, Day 1	Week 8 +2 weeks (+4 weeks in case of reversible toxicity), Day 1	
	Visit 2, Day 2	Day 2	
	Visit 2, Day 3	Day 3	
	Visit 2, Day 4	Day 4(-Day 5)	
	Visit 2, Day 7	Day 7(- Day 8)	
	Visit 2, Day 15	Day 15 ±2 days	
	Follow-up 1 Visit 2	Week 12 (Day 29±5)	
	Follow-up 2 Visit 2 - Part B only	Week 14 (Day 42±5)	
	Visit 3, Day 1	Week 16 +2 weeks (+4 weeks in case of reversible toxicity), Day 1	
	Visit 3, Day 2	Day 2	
	Visit 3, Day 3	Day 3	
	Visit 3, Day 4	Day 4(-Day 5)	
	Visit 3, Day 7	Day 7(- Day 8)	
	Visit 3, Day 15	Day 15 ±2 days	
	Follow-up 1 Visit 3	Week 20 (Day 29±5)	
	Follow-up 2 Visit 3 – Part B only	Week 22 (Day 42±5)	
	End Of Core-Trial (EOCT)	End of Core-Trial Visit	Week 24 (Day 1±5)

Study part	Scheduled visit	Time interval (days)
Additional Cycles – Part B only	Additional Cycle 4, Day 1	Week 24 + 2 weeks (+4 weeks in case of reversible toxicity), Day 1
	Additional Cycle 4, Day 2	Day 2
	Additional Cycle 4, Day 3	Day 3
	Additional Cycle 4, Day 4	Day 4(-Day 5)
	Additional Cycle 4, Day 7	Day 7(- Day 8)
	Additional Cycle 4, Day 15	Day 15 ±2 days
	Follow-up 1 Additional Cycle 4	Week 28 (Day 29±5)
	Follow-up 2 Additional Cycle 4	Week 30 (Day 42±5)
	Additional Cycle 5, Day 1	Week 32 + 2 weeks (+4 weeks in case of reversible toxicity), Day 1
	Additional Cycle 5, Day 2	Day 2

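### The SAP's EOCT visit window makes no allowance for permitted dosing delays, so one 2-week extension takes the EOCT visit out of its own window

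*Protocol*

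**What the plan says.** The protocol treats its week numbers as nominal. Section 5.2 states: "If the time buffers of the visits are utilised, later visits must be shifted accordingly". Section 5.2.8 says "The EOCT Visit should take place 8 weeks after Visit 3", and gives Week 24 only "if no previous visit window was extended". The follow-up visits in sections 5.2.3, 5.2.5 and 5.2.7 carry the same condition. For Visit 3, section 5.2.6.1 adds "otherwise Week 16 should be changed to the appropriate week number".

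The SAP's descriptive sections agree. Section 1.3.1.1 gives cycles "with an interval of 8 weeks +2 weeks, or up to +4 weeks in case of AEs which have not adequately recovered", so the extension applies to each interval. Section 1.2.1 places EOCT 8 weeks (±5 days) "after Visit 3 Day 1, the safety and efficacy of the treatment will be evaluated".

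SAP section 3.2.14 then sets the windows used for analysis. It says that "time intervals (e.g. visit windows) have been constructed so that every observation collected can be allocated to a particular time point". The table's rows are of mixed kinds:

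- Days 2 to 15 are days within a cycle.
- Follow-up rows give both a week number and a cycle day (29 or 42).
- Visit 3 Day 1 is "Week 16 +2 weeks (+4 weeks in case of reversible toxicity), Day 1". The Cycle 4 and Cycle 5 Day 1 rows have the same form, from Week 24 and Week 32.
- EOCT is Week 24, Day 1 ±5.
- The end-of-additional-cycles and early-withdrawal rows count from the last dose.

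The table does not repeat the protocol's condition and gives no rule for re-anchoring after a delay.

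**The concern.** The EOCT row has neither a delay allowance nor a cycle anchor. The Day 1 rows for Visit 3 and Cycles 4 and 5 hold one extension in total, while the schedule permits one per interval. A subject who follows the protocol exactly, but uses a buffer, can therefore have an EOCT visit that the SAP table does not recognise as EOCT.

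The outputs at stake are the by-visit summaries: laboratory values (SAP 3.2.1.3), vital signs (3.2.1.4), Karnofsky score (3.2.1.8), and sum of diameters and quality of life (3.2.3). Quality-of-life change from baseline to EOCT is a named secondary endpoint (Protocol 3.2.2.5). Records that leave the EOCT window would be missing from the EOCT column or carry another visit's label.

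**Working it through.** **Convention.** First dose is study Day 1 and there is no Day 0 (SAP Appendix 1, item 16), so Week w falls on day 7w + 1.

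**Plan's own figure.** Three 8-week intervals give Week 24, which is day 7 × 24 + 1 = 169. The SAP window is 169 ± 5 = days 164 to 174. Without a delay the table reproduces the protocol.

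**One 2-week extension, at Visit 2 or Visit 3.**

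- Visit 3 Day 1: Week 18, day 127. Its row runs from day 113 (Week 16) to day 127, so it stays inside.
- EOCT: 127 + 56 = day 183, permitted range 178 to 188. The SAP window ends on day 174, so there is no overlap.
- Part A: there is no Cycle 4 row, so the EOCT visit has no window.
- Part B: Cycle 4 Day 1 runs from Week 24 to Week 26, days 169 to 183, or to day 197 with the 4-week allowance. Day 183 is the last day of the shorter window. Of the 11 permitted EOCT days, 6 (178 to 183) lie in the shorter window and all 11 in the longer.

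**Smallest delay that matters.** An EOCT visit held exactly 8 weeks after Visit 3 leaves the window once total delay exceeds 174 − 169 = 5 days. The whole ±5-day range is outside once total delay exceeds 174 − 164 = 10 days.

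**More than one extension.**

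| Row | Permitted delays | Actual | Latest day in SAP row |
|---|---|---|---|
| Visit 3 Day 1 | +2 weeks twice | Week 20, day 141 | 127, or 141 with the toxicity allowance |
| Visit 3 Day 1 | +4 weeks twice | Week 24, day 169 | 141 |
| Cycle 4 Day 1 | +2 weeks three times | Week 30, day 211 | 197 |
| Cycle 5 Day 1 | +2 weeks four times | Week 40, day 281 | 253 |

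For Visit 3, two extensions that need no adverse event already use the whole toxicity allowance. For Cycles 4 and 5, repeated 2-week extensions pass even that.

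**Follow-up rows, after one 2-week extension.** The result depends on which half of the cell is used.

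- Week number read literally: the Part B Week-6 visit after Visit 3 is due on 127 + 41 = day 168 (163 to 173). Ten of its 11 permitted days lie in the EOCT window, and day 168 is one day from the EOCT target of 169. In Part A the only follow-up after Visit 3 is due on 127 + 28 = day 155, outside the EOCT window.
- Cycle day (29 or 42) used: the follow-up rows are correct in both parts.

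**After re-anchoring.** With the same 2-week extension, the Week-6 window is days 163 to 173 and the EOCT window is days 178 to 188. Each contains its own visit and they do not overlap.

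**The case against.** The strongest reply is that SAP 3.2.14 opens by tying the analysis to the protocol's schedule and sends off-schedule results to whichever visit fits best. The protocol's schedule includes the shifting rule, SAP 1.2.1 anchors EOCT correctly, and the section closes by restating the 8 (+2)-week interval between cycles. A sensible programmer might reach the right answer. This shows that the intended timing is recoverable. It does not repair the table, because the section presents the windows as the means of making that allocation. The EOCT window as written excludes a visit held on time.

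Several stronger readings are tempting, and the documents do not support them:

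- *The whole table is fixed weeks from first dose.* It is mixed, and many rows are cycle-relative or include a buffer.
- *A follow-up visit will be reported as EOCT.* That needs the literal week reading. After one 2-week extension it is limited to Part B, and the visit text for Week 22 (Protocol 5.2.7) lists laboratory tests only. CT, Karnofsky and quality-of-life records could drop out of EOCT, but that visit would not replace them.
- *The overlap of EOCT with Cycle 4 Day 1 is itself an error.* It exists without any delay (days 169 to 174) and is partly by design, since the two visits may be combined.
- *The toxicity assessment is distorted.* DLTs, adverse event periods counted from the last dose, nadir by cycle and worst-grade shifts do not use these windows. A 2-week extension needs no adverse event, so displaced subjects are not only those with toxicity. Protocol 1.4 reports when severe haematological toxicity began in the investigator study, not when counts were lowest.

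**Conclusion.** The point holds for the EOCT row and for the Day 1 rows of Visit 3 and Cycles 4 and 5. These rows conflict with the protocol's shifting rule and with the SAP's own definition of EOCT. One permitted 2-week extension moves EOCT to day 183 against a window ending on day 174. In Part A the visit is left without a window. In Part B it lands in a Cycle 4 window, and the table does not restrict that window to subjects who received Cycle 4. For the follow-up rows the finding is an ambiguity: wrong if the week number governs, right if the cycle day does.

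The consequence is confined to by-visit descriptive summaries. The conclusion assumes that the windows are applied as written and that recorded visit labels do not override them; the SAP states no such override. The documents do not say how many subjects were delayed, so the number of affected records cannot be given. This should be corrected before the by-visit tables are produced, but it does not threaten the main safety outputs.

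**What to change.** Revise SAP section 3.2.14 as follows:

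- Count each follow-up window from the actual Day 1 of its own cycle.
- Define EOCT as 56 ± 5 days after the actual Visit 3 Day 1.
- Assign cycle Day 1 records by the actual infusion.
- Mark the week numbers as holding only where there was no previous extension.
- Apply Cycle 4 and 5 windows only to subjects dosed in those cycles.
- State how a combined EOCT and Cycle 4 Day 1 visit is labelled. Re-anchoring alone does not settle this, because both are due 8 weeks after Visit 3.

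The cost is SAP wording and a programming change to the visit derivation. No visit, dose or clinical rule changes.

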5.2.1 Screening Visit

Week -4 to -1

Depending on the SRS, a hospitalisation of up to 2 days may be necessary.

- written informed consent
 - study informed consent and optional informed consent for biobanking
- clinical assessments
 - demographic details
 - medical history and concurrent (baseline) conditions
 - concomitant and prior medications (taken up to 28 days before the Screening Visit)
 - physical examination
 - height
 - vital signs and 12-lead ECG
 - clinical laboratory tests (biochemistry, haematology, and urinalysis)
 - circulating tumour marker (blood)
 - serum β -human chorionic gonadotropin (HCG) pregnancy test for women of childbearing potential (not surgically sterile or 2 years postmenopausal)
 - review of inclusion and exclusion criteria.
 - performance status.
- CT/MRI (not older than 1 month on the first day of the Screening Visit)
- sstr scan (unless already performed within 6 months of Visit 1 Day 1)
- CCI

5.2.2 Visit 1

During Visit 1, patient may be hospitalised on Day 1 for 24 hours and up to Day 8. The duration of the hospital stay is left at the discretion of the investigator and will depend on the individual subject and the regulatory requirements at the study site. Later assessments can be performed on an outpatient basis.

All postdosing time points are defined from stop of infusion (0).

5.2.2.1 Visit 1, Day 1 (Week 0)

Safety assessments (predosing results must be checked before ¹⁷⁷Lu-OPS201 administration; these can be performed 1 day before administration)

- physical examination
- weight
- vital signs and 12-lead ECG
- performance status
- clinical laboratory tests (biochemistry, haematology, pituitary marker and urinalysis)
- serum β -HCG or urine pregnancy test for women of childbearing potential (not surgically sterile or 2 years postmenopausal)
- AEs/concomitant medications
- 24 hour ECG (Holter) (to start before amino acid infusion).

Efficacy assessments

- Quality of Life Questionnaire (QLQ-C30; GI.NET21)
- tumour markers.

CCI

Administration of ¹⁷⁷Lu-OPS201

See Section 6.2.

Safety assessments (postdosing)

- vital signs (stop of infusion, 0.5 hours \pm 5 minutes, 1 hour \pm 10 minutes, 4 hours \pm 10 minutes)
- AEs/Concomitant medications

Dosimetric measurements

- blood sampling (2 mL) before and at stop of infusion (0) and 5 minutes \pm 1 minute, 0.5 hours \pm 3 minutes, 1 hour \pm 5 minutes, 4 hours \pm 10 minutes postinfusion
- whole body imaging at 4 hours \pm 10 minutes
- SPECT/CT imaging (Part B only) at 4 hours \pm 10 minutes
- urine collection 0 to 6 hours and 6 to 24 hours postinfusion (Part A), 0 (start of the infusion) to 4 hours, 4 to 24 hours postinfusion at visit 1 only (0 (start of the infusion) to 4 hours only for US and Canada sites) (Part B)

OPS201 PK assessments (Part B only)

- blood samples for assessment of OPS201 plasma levels will be collected at the following time points at visit 1 only: before the infusion (baseline), at the end of the infusion (0), 5 minutes \pm 1 minute, 30 minutes \pm 3 minutes, 60 minutes \pm 5 minutes and

4 hours±10 minutes, 6 hours±30 minutes, and 8 hours±30 minutes after the administration of ¹⁷⁷Lu-OPS201.

- urine collection for assessment of OPS201 urine levels will be collected at the following time periods at visit 1 only: from 0 (start of the infusion) to 4 and 4 to 24 after the start of infusion (0 (start of the infusion) to 4 hours only for US and Canada sites).

CCI

Efficacy assessments

- Survival

5.2.2.2 Visit 1, Day 2

Safety assessments (at 24±1 hour)

- clinical laboratory tests (biochemistry, haematology, pituitary marker)
- vital signs
- AEs/concomitant medications.

Dosimetric measurements (at 24±1 hour)

- blood sampling at 24±1 hours
- whole body imaging
- SPECT/CT imaging
- urine collection 24 to 48 hours postinfusion at visit 1 only (not applicable for US and Canada sites)

OPS201 PK assessments (Part B only)

- blood samples for assessment of OPS201 plasma levels will be collected 24 hours (±1 hour) after the administration of ¹⁷⁷Lu-OPS201 at visit 1 only.
- urine collection for assessment of OPS201 urine levels will be collected from 24 to 48 hours after the start of infusion at visit 1 only (not applicable for US and Canada sites).

CCI

5.2.2.3 Visit 1, Day 3

Safety assessments (at 48 hours±1 hour)

- clinical laboratory tests (biochemistry, haematology)
- Vital signs
- AEs/concomitant medications.

Dosimetric measurements (at 48 hours±1 hour)

- blood sampling
- whole body imaging
- SPECT/CT imaging (Part B only)
- urine collection 24 to 48 hours at visit 1 only (continued) (not applicable for US and Canada sites).

OPS201 PK assessments (Part B only)

- blood samples for assessment of OPS201 plasma levels will be collected 48 hours (± 1 hour) after the administration of ^{177}Lu -OPS201 at visit 1 only.
- urine collection for assessment of OPS201 urine levels will be collected 24 to 48 hours at visit 1 only (continued) (not applicable for US and Canada sites).

CCI

5.2.2.4 Visit 1, Day 4 (-Day 5)**Safety assessments (at 72 to 96 hours)**

- laboratory tests (biochemistry, haematology)
- vital signs
- AEs/concomitant medications.

Dosimetric measurements (at 72 to 96 hours)

- blood sampling
- whole body imaging
- SPECT/CT imaging (Part B only).

CCI

5.2.2.5 Visit 1, Day 7 (-Day 8)**Safety assessments (at 144 to 168 hours postinfusion)**

- clinical laboratory tests (biochemistry, haematology and urinalysis)
- vital signs
- AEs/concomitant medications.

Dosimetric measurements (at 144 to 168 hours postinfusion)

- blood sampling
- whole body imaging
- SPECT/CT imaging (Part B only).

CCI

5.2.2.6 Visit 1, Day 15 (± 2 Days)**Safety assessments**

- clinical laboratory tests (biochemistry, haematology and urinalysis)
- vital signs
- AEs/concomitant medications.

5.2.3 Follow-up Visit 1

Follow-up Visit 1 should be Week 4 (Day 29 ± 5) and Week 6 (Day 42 ± 5) if no previous visit window was extended. At Week 6, only safety assessments such as clinical laboratory tests (biochemistry, haematology and urinalysis) will be performed.

5.2.3.1 Week 4 (Day 29±5)

Safety assessments

- physical examination
- clinical laboratory tests (biochemistry, haematology, and urinalysis)
- vital signs and 12-lead ECG
- AEs/concomitant medications.

Efficacy assessments

- survival
- tumour markers.

CCI

5.2.3.2 Week 6 (Day 42±5) - Part B only

Safety assessments

- clinical laboratory tests (biochemistry, haematology and urinalysis)

5.2.4 Visit 2

During Visit 2, patient may be hospitalised on Day 1 for 24 hours and up to Day 4. The duration of the hospital stay is left at the discretion of the investigator and will depend on the individual subject and the regulatory requirements at the study site. Later assessments may be performed on an outpatient basis.

5.2.4.1 Visit 2, Day 1 (Week 8 (+2 Weeks or Up to +4 Weeks in Case of AEs which have Not Adequately Recovered))

Safety assessments (predosing results must be checked before ¹⁷⁷Lu-OPS201 administration; can be performed one day before)

- physical examination
- weight
- vital signs and 12-lead ECG
- performance status
- clinical laboratory tests (biochemistry, haematology, and urinalysis)
- serum or urine pregnancy test for women of childbearing potential (not surgically sterile or 2 years postmenopausal).
- AEs/concomitant medications
- control of withdrawal from treatment criteria (see Section 6.4)
- 24-hour ECG (Holter) (to start before amino acid infusion).

Efficacy assessments

- survival
- quality of life questionnaire (QLQ-C30; GI.NET21)
- tumour markers
- CT/MRI (same method as in Screening Visit); +2 weeks or up to +4 weeks in case of AEs

CCI

CCI

Administration of ¹⁷⁷Lu-OPS201

See Section 6.2.

Safety assessments (postdosing)

- vital signs (stop of infusion, 30±5 minutes 60±10 minutes, 4 hours ±10 minutes)
- AEs/concomitant medications.

Dosimetric measurements

- blood sampling before and at stop of infusion at 60±5 minutes, 4 hours ±10 minutes
- whole body imaging at 4 hours ±10 minutes.
- SPECT/CT imaging (Part B only) at 4 hours ±10 minutes.

